#### *Outcomes derived from clinical EHR records*

##### Dialysis treatment schedule adherence (mean minutes missed per month)

This outcome will be summarized as total minutes prescribed per month, minutes delivered per month and the missed minutes is the prescribed minus the delivered minutes. There will be no value less than zero (eg. no accounting for additional minutes).

This is a repeated end-point with values for each month of the observation period (Months 1 through up to 18). The value itself is interval (0 – 240, or higher).

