2) To test the effects of a telephone-based peer mentor intervention on adherence behaviors, perception of self-efficacy, perception of social support and overall nutrition as possible mediators in the association of this intervention with primary outcomes	Month 3 & M-12 to 18 (T2) Intervention compared to UC a) Mean weekly missed minutes of dialysis; b) Mean monthly IDWG; c) Serum Alb; d) Self-efficacy; e) Social support; f) Knowledge	The effects of the peer intervention on adherence behaviors and perception of social support may alter the causal pathway(s) of high hospitalization rates in hemodialysis. Studies have shown an association between lack of patients' engagement and social support and adherence behaviors in patients on hemodialysis. Further studies have established the strong association between adherence behaviors and incidence of hospitalizations in this population.	Low perception of social support and low self-efficacy are associated with adherence behaviors and hospitalization outcomes.
Tertiary/Exploratory			
To test the feasibility and fidelity of a peer training program on mentor uptake	a. Attendance records of training sessions; b. Formative assessments of each training session	To inform future dissemination by characterizing the structural elements of the training program methods	n/a
To test the feasibility of the telephone-based intervention on mentees assigned to the intervention group	a) number and duration of telephone contact made by mentor/mentee; b) self-recorded content of mentor/mentee conversations;	Telephone records serve as the primary data to determine total dosing of intervention (minutes), as well as pattern of contact over the 3-month period	n/a

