### Patient Participants [Intervention or Usual Care]

Patient participants must meet all of the following inclusion criteria:

1. Provision of signed and dated informed consent form
2. Stated willingness to comply with all study procedures, including randomization, and availability for the duration of the study
3. Males and females; Age > 21 years
4. Dialysis treatment at one of the participating dialysis units
5. One of the following criteria:

- a. Diagnosis of ESKD and treatment with in-center hemodialysis for less than 90 days
- b. One or more hospitalizations in the prior month
- c. One or more ED visits in the prior month
- d. More than 1 unexcused missed dialysis treatments in the prior month
- e. 2 or more shortened (more than 10 minutes) dialysis treatments in the prior month
- f. Use of a catheter for dialysis access
- g. An average of more than 4% IDWG in any week during the prior month
- h. Serum albumin less than 3.5 mg/dL in the prior month
6. Fluent in English (or Spanish – Bronx, NY site)

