#### 9.4.3 ANALYSIS OF THE SECONDARY ENDPOINT(S)

The primary evaluation will be at the end of the study period (12 to 18-months) using all available data regardless of the period end for participants, and comparisons at 3M will be secondary. For the primary evaluation, we will test the longitudinal effect of a peer mentor led telephone intervention on mentee self-management skills including 1) dialysis adherence (mean number of outpatient dialysis hours per month), 2) mean monthly inter-dialytic weight gain (IDWG), and 3) mean monthly albumin levels. We

will compare the rate of change over time of the monthly secondary endpoints between two intervention groups using linear mixed effects regression model. In the regression model, the secondary endpoint (e.g. monthly mean dialysis hours) is the outcome variable with two main effects (the intervention assignment and months from baseline) and the interaction term between the main effects. The interaction term (i.e. the difference in slopes between two groups) is the primary predictor of interest. There will be three random intercepts to account for mentor effect, facility effect (out of seven facilities) and subject effect (to account for within correlation from repeated measurements). We will evaluate differences in baseline variables identified in Table 6 and if they are different between the groups, we will adjust for them as confounders.

For the secondary evaluation at 3M, we will perform Wilcoxon rank-sum test to compare the 3-months change of secondary endpoints between the intervention mentee and control mentees. To account for confounders, we will also fit linear regression model with two random intercepts. In the regression model, the 3 months-change of secondary endpoint is the outcome variable and the intervention assignment of the mentees is the primary binary predictor. The random intercepts will account for the correlation between mentees who share a common mentor as well as the correlation between mentees who are from a common dialysis facility.

Below, each endpoint is described including its source, scoring and planned analysis approach. Additional details for scoring of surveys is provided in the PEER HD Survey Scoring guide document. Within group (mentors) for change in outcomes over time will also be evaluated.

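### The dialysis adherence endpoint has no rule for hospital days, so fewer admissions could be read as better adherence

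*Combined protocol and SAP*

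**What the plan says.** The outcome subsection of Section 9.4.3 on treatment schedule adherence totals prescribed and delivered minutes for each month, and "the missed minutes is the prescribed minus the delivered minutes". The only further rule is that a value may not fall below zero. The opening of Section 9.4.3 lists the outcome among self-management skills but measures it as "mean number of outpatient dialysis hours per month". Table 3 in Section 3 uses weekly missed minutes, and Sections 1.1 and 9.1 use monthly missed minutes.

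None of these places mentions hospital days, inpatient dialysis or excused absence. The plan does make such a distinction for eligibility: one patient criterion in Section 5.1 is "More than 1 unexcused missed dialysis treatments in the prior month".

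Table 3 lists missed minutes under an objective that looks at adherence behaviours and related measures "as possible mediators in the association of this intervention with primary outcomes". The primary outcome is the composite count of ED visits and hospitalizations (Section 9.4.2). The monthly record review in Section 8.1 collects prescribed and delivered treatment duration together with ED visits and unplanned hospitalizations, but no text links the two.

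**The concern.** A patient in hospital on a dialysis day does not attend the outpatient unit. In the outpatient-hours form, read as hours delivered, that session is lost. In the prescribed-minus-delivered form it becomes missed time on two conditions: prescribed minutes continue to accrue during the stay, and inpatient treatment is not counted as delivered. In both cases an admission registers as poorer adherence, whatever the patient's self-management.

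The intervention aims to reduce admissions. If it does so by any route, the adherence endpoint could improve with it and be reported as a behavioural effect. An ED visit without admission adds to the overlap only if it displaces a session.

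**Working it through.** The plan states no sample size, power or expected value for the adherence endpoint, so there is no figure to reproduce. The check is how much an admission alone could move it.

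**Inputs**
- Admissions: 2 per year (Section 2.2.1), so 2/12 = 0.167 per patient-month.
- Reduction: 20%, the effect in Section 9.2 for the composite, applied here to admissions.
- Outpatient sessions lost per admission: 1 to 3 (assumed; no length of stay is given).
- Minutes per session: 240 (assumed; Section 9.4.3 gives only a range of values).
- Sessions per month: 13 (assumed, 3 × 52/12).
- Sessions skipped 8% and shortened 20% (Section 2.2.3); 20 minutes per shortening (assumed).

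**Step 1. Missed minutes added by admissions** = admissions per month × sessions lost × 240. The artefact from a 20% cut is 0.20 times that.

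| Sessions lost per admission | Added per month | Artefact per month |
|---|---|---|
| 1 | 0.167 × 1 × 240 = 40 min | 8 min |
| 2 | 0.167 × 2 × 240 = 80 min | 16 min |
| 3 | 0.167 × 3 × 240 = 120 min | 24 min |

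On the outpatient-hours scale the artefact is 8/60 = 0.13 to 24/60 = 0.40 hours per month.

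**Step 2. Sensitivity to the admission rate.** The 0.27 events per month in Section 9.2 combine ED visits and hospitalizations.
- If half are admissions (0.135): 32.4 to 97.2 minutes added, artefact 6.5 to 19.4.
- If all are admissions (0.27, an upper bound): 64.8 to 194.4 minutes added, artefact 13.0 to 38.9.

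**Step 3. Share of all missed minutes.** Skipping gives 0.08 × 13 × 240 = 249.6 minutes and shortening gives 0.20 × 13 × 20 = 52, together 301.6. At 2 admissions per year the hospital share is 40/341.6 = 12% to 120/421.6 = 28%.

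**Step 4. Association with the primary outcome.** A simulation used Poisson composite events at 0.27 per month, of which about 0.167 were admissions. Skipping and shortening were generated independently of events. Monthly missed minutes still correlated with the composite count at about 0.30 (1 session lost) to 0.61 (3 sessions). The simulated patients were identical; real differences between patients would change these values.

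**Step 5. Which planned comparison is exposed.** The main test in Section 9.4.3 is the group-by-month interaction, a difference in slopes. A steady fall in admissions is a shift in level, which goes mostly into the group main effect. It enters the slope only to the extent that the effect on admissions grows or fades over follow-up. The 3-month change analysis, which Section 9.4.3 calls secondary, and any comparison of group means would carry it directly. The hypothesis in Section 9.1 is itself worded as a comparison of end-of-study values.

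**The case against.** The protocol does not say that hospital sessions count as missed. It leaves open whether prescribed minutes accrue during a stay and whether inpatient treatment is credited. The manual of procedures, to which it refers for form instructions, is not among the documents and may settle this. That stands for the missed-minutes form. It does not rescue the outpatient-hours form, where a displaced session reduces the count under the wording given. A rule that decides what the endpoint measures also belongs in Section 9.4.3.

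A reader might infer that the trial plans a circular mediation analysis. The documents do not support this. Table 3 speaks only of possible mediators, Section 9 contains no mediation model for adherence, and the mediator or moderator analyses in Section 9.4.9 concern dose and mentor–mentee concordance.

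A reader might also conclude that a quarter to a third of missed minutes are hospital days. That depends on an assumed stay length and on leaving out shortened sessions. The trial population adds uncertainty in both directions: selecting patients who miss or shorten sessions lowers the share, and selecting recently hospitalized patients raises it.

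Finally, removing hospital days conditions on a post-randomization event that the intervention may change, and total missed outpatient minutes is a legitimate intention-to-treat quantity. This is fair and is the reason to keep the unadjusted version as a sensitivity analysis. But total missed minutes describes treatment received at the unit, whereas Section 9.4.3 presents the outcome as a self-management skill. The version without hospital days is closer to that.

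**Conclusion.** The point holds as a defect in the definition of a secondary endpoint. With no rule for hospital days, an admission lowers outpatient hours and, under a plausible but unconfirmed reading, raises missed minutes. Fewer admissions could therefore look like better adherence.

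At 2 admissions per year the possible artefact is 8 to 24 minutes per month, or 6.5 to 39 over the wider range of admission rates. These sizes rest on the assumed sessions lost and session length, and on a 20% reduction applied to admissions. For outpatient hours the direction does not depend on those values; for missed minutes it requires the two conditions on prescribing and crediting. The consequence is greatest for the 3-month change and group means and smaller for the slope test. The documents do not show that the slope test is invalid or that the primary analysis is affected.

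**What to change.** In Section 9.4.3:
- Remove sessions scheduled between admission and discharge from both prescribed and delivered minutes.
- Analyse missed minutes per prescribed outpatient minute.
- Report the unadjusted version as a sensitivity analysis.
- Use one definition and unit in Table 3, the opening of Section 9.4.3 and its outcome subsection, matching Sections 1.1 and 9.1.

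In Section 8.1, record admission and discharge dates in the monthly review and include planned stays. The current text mentions no discharge dates and covers only unplanned hospitalizations. If adherence is later examined as a possible mediator, use the version that excludes hospital days.

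The cost is a wording change, a small amount of extra abstraction, and slightly fewer minutes per patient in the analysis.

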##### Inter-dialytic weight gain (IDWG) (mean monthly, %)

This outcome will be summarized each month as the mean IDWG for the month prior in kilograms. The value will include all intervals regardless of time between treatments (2-days, 3-days or other), and will be calculated as the pre-weight minus the prior treatment post-weight. Prescribed dry weight will also be collected monthly to permit an average calculation of % of dry weight. This value is interval.

##### Nutritional status (serum albumin g/dL)

The serum albumin collected for monthly labs will be collected. If there are multiple values in one calendar month, then the last value of the month will be collected. This is an interval variable.

#### *Outcomes derived from patient-reported measures*

##### Dialysis knowledge {CHeKS; CHeKS PLUS}

See scoring guide for full detail. These are multiple choice knowledge questionnaires where there is only one correct answer. The score will be % correctly answered of the total. Missing responses are scored as incorrect. At least 75% of the items must have answer to be scored.

##### Dialysis self-management self-efficacy

The PDialSMS is collected at three times during the study. It is an interval value ranging from 8 to 40.

##### Social support

This is measured with the 12 item Multidimensional Scale of Perceived Social Support (MSPSS). The total score is the sum across the 12 items (each 1-7) divided by 12. There are also 3 subscales (significant other, family, and friends) each composed of 4 items. This value is interval.

A dialysis-specific social support survey is also collected to characterize the frequency of interactions between the participant and other dialysis patients. There are six items (range 1-5) and the total score is the mean of the six items.

#### Quality of life

This is measured with the RAND SF-36. Responses are standardized to a 0 to 100 scale and then averaged together to derived 8 subscale scores. Four of these then contribute to the physical component score (PCS), and four contribute to the mental component score (MCS). All values are interval.

For the perception of social support and self-efficacy we will use linear regression with two random intercepts to compare the scores on the PKDSMS, social support survey and quality of life surveys between the intervention mentee and control mentees at the various time points. The outcome variable for the regression is the assessment scores and the predictor of interest is the binary indicator of intervention groups.

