## 9.3 POPULATIONS FOR ANALYSES

For the primary endpoint comparison, an intention-to-treat analysis will be used, including all available data on randomized participants. It is expected that up to 20% of randomized participants may discontinue from the study prior to the end point. These participants will be included in the primary analysis and data from the monthly outcome ascertainment up until the last available time point will be used. As preparation for the follow-up period modification, events to date were evaluated at one site (Einstein) and were found to be more frequent than initial estimates. This informed the request for reduction in the follow-up period.

The characteristics of those who do not complete all study activities will be compared to those with complete follow-up to examine for potential biases introduced by differential follow-up among the two groups. These will be considered ancillary analyses.

Secondary analyses will examine additionally an as-treated population. This will group any intervention patient who did not participate in more than 20 minutes total of the intervention during the three-month period to be classified as the usual care group.

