All data analyses will be preceded by extensive data checking and verification to identify and resolve the reasons for missing values, inconsistencies, and out-of-range values. Although, we anticipate less than 15% missing data, we will carefully examine whether missingness is completely at random (MCAR), at random (MAR) or informative (MNAR). Models proposed for analysis can handle incomplete data (i.e. entire subject is not deleted if missing data at one time point), but do require at least that missingness be at random. Modelling will consider using multiple imputation techniques of covariates to reduce potential biases.

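### The survey-score model names no visit term and no patient effect, so on its natural reading the T2 comparison ignores the known earlier scores of patients without a T2 survey

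*Combined protocol and SAP*

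**What the plan says.** Section 8.1 schedules the patient surveys at baseline, month 3 and T2 (12 to 18 months). For the self-efficacy, social support and quality-of-life scores, the last paragraph under Quality of life in section 9.4.3 says "we will use linear regression with two random intercepts to compare the scores on the PKDSMS, social support survey and quality of life surveys". As to timing, it sets no single visit: the two arms are to be compared at several unnamed visits, and "the predictor of interest is the binary indicator of intervention groups". Section 9.4.1 adds site to every analysis. No visit term, arm-by-visit term or patient effect is named.

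That paragraph does not define its two intercepts. For the 3-month change model, section 9.4.3 does: "The random intercepts will account for the correlation between mentees who share a common mentor as well as the correlation between mentees" from the same facility. Section 9.4.2 uses the same pair for the primary endpoint. For the monthly endpoints (dialysis adherence, weight gain, albumin), section 9.4.3 goes further: "There will be three random intercepts to account for mentor effect, facility effect (out of seven facilities) and subject effect", together with month and arm-by-month terms.

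On missing data, section 9.4.2 says in general terms: "Models proposed for analysis can handle incomplete data (i.e. entire subject is not deleted if missing data at one time point". It adds that missingness at random is the least these models require, and it mentions multiple imputation for covariates only. Section 9.4.3 makes end of study the main evaluation of the secondary endpoints and says that all available data will be used.

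**The concern.** The incomplete-data property described in section 9.4.2 belongs to likelihood models that hold several scores per patient and link them through a patient effect or a within-patient covariance. The survey paragraph describes no such model, and the plan does not say whether the visits are analysed separately or together.

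If separately, a patient with baseline and 3-month scores but no T2 score contributes nothing to the T2 estimate. That estimate is valid only if, within arm, a missing T2 score is unrelated to what the score would have been. Drop-out that depends on the 3-month score would satisfy missing at random in a joint model, but it can bias a T2-only comparison when the dependence differs by arm. If the visits are pooled, correlation within patients is left unmodelled.

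At stake is the end-of-study comparison of the patient-reported outcomes, which section 9.4.3 treats as the main evaluation of secondary endpoints. Patients who die or are lost after month 3 are those whose known scores would go unused.

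**Working it through.** **Plan's own figure.** The documents give no power or precision for any survey score. The power statement in section 9.2 concerns the event rate and is not an input here.

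**Inputs from the documents**
- 100 patients per arm (9.2).
- Three candidate missingness figures: under 15% missing data (9.4.2); 20% from section 9.3 ("It is expected that up to 20% of randomized participants may discontinue from the study prior to the end point"); 25% drop-out in the sample size (9.2). None is a T2 survey rate, so I use them as a range.
- Two-sided 0.05 (9.4.1).

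**Assumed, not in the documents**
- Correlation between a patient's scores: 0.3–0.7.
- Strength of the link between 3-month score and drop-out: log-odds 1 per SD.

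**Step 1. Terms in each model**

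| Model (9.4.3) | Time terms | Random intercepts |
|---|---|---|
| Monthly endpoints | month, arm-by-month | mentor, facility, subject |
| 3-month change | none (single change score) | mentor, facility |
| Survey scores | none named | two, taken as mentor and facility |

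**Step 2. Separate models: who is lost.** A patient without T2 leaves the T2 comparison and stays in the 3-month one. Of 100 per arm, 85, 80 or 75 remain at T2. In the change model ("the 3 months-change of secondary endpoint is the outcome variable") a patient needs both scores.

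**Step 3. Separate models: precision.** The standard error (SE) ratio to complete data is 1/√(1−m):
- 1/√0.85 = 1.08
- 1/√0.80 = 1.12
- 1/√0.75 = 1.15

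For an assumed effect of 0.4 SD, power falls from 0.81 to 0.74, 0.72 or 0.69.

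**Step 4. Separate models: bias with no true effect.** In one arm let logit P(T2 missing) = a + Z, where Z is the standardised 3-month score and a is set to give m. In the other arm drop-out is unrelated to Z. Bias = correlation × mean of Z among those retained. That mean is 0.133, 0.173 or 0.213 SD away from zero at m = 15, 20 or 25%.

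| m | correlation 0.5 | correlation 0.7 |
|---|---|---|
| 15% | 0.07 SD | 0.09 SD |
| 20% | 0.09 SD | 0.12 SD |
| 25% | 0.11 SD | 0.15 SD |

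With log-odds 1 in one arm and 0.5 in the other, at 25%, the bias is 0.05–0.07 SD. With the same dependence in both arms it is about 0.

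**Step 5. Pooled model.** If patient correlation ρ is wholly ignored with k scores each, type I error = 2[1 − Φ(1.96/√(1+(k−1)ρ))]. For ρ from 0.3 to 0.7 this is 0.086–0.133 for k = 2 and 0.121–0.206 for k = 3. The planned model has a mentor intercept, which changes the result. Simulation (1,500 runs, 17 mentors, facility as a fixed effect) gave:
- controls given no mentor effect: 0.06–0.10 (k = 2) and 0.09–0.11 (k = 3);
- each control coded as its own mentor cluster: 0.01–0.04 (k = 2), which is conservative.

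The plan does not state this coding, so neither the size nor the direction of the error is fixed.

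**Step 6. What a joint model gains.** In a missing-at-random simulation (4,000 runs, 15–25% missing, correlation 0.3–0.7) the observed-only T2 contrast was off by 0.05–0.17 SD. The likelihood estimate using baseline and 3-month scores was off by at most 0.005 SD. On precision at 25% missing, the observed-only SE is √(2/75) = 0.163 SD. Linking the visits alone gives 0.157 (correlation 0.5) or 0.152 (0.7). Constraining the baseline means to be equal as well gives about 0.14 or 0.11. Most of the precision gain therefore comes from using baseline, and the protection against bias comes from linking the visits.

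**The case against.** A separate comparison at each visit is a common analysis, and several provisions limit the harm. Surveys continue after the intervention is stopped (7.1). Patients discontinued from the study get the T2 surveys then, if able and willing (7.2). Section 9.3 compares completers with non-completers. Section 9.4.2 offers a sandwich estimator if the random-effects structure is misspecified. The bias figure needs drop-out to be tied to the score differently by arm, and nothing in the documents points to such a pattern.

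A reader might also infer three stronger things, which the documents do not support:
- **That the model discards anyone who misses a visit, so that section 9.4.2 is flatly contradicted.** With one model per visit the patient is lost only from the missed visit's comparison. The statement is that the entire subject is not deleted, and missing at random is given there as a minimum, not as sufficient.
- **That repeated scores will be treated as independent.** This needs pooling, the less natural reading. Section 9.4.3 separates the end-of-study evaluation from the 3-month one, and a single pooled arm coefficient would give neither.
- **That p-values would be too small, with type I error of 10–20%.** Figures of that size leave out the mentor and facility intercepts. Once a mentor intercept is included the error can go either way.

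What remains is that the mitigations reduce missing T2 scores without removing them (deaths and patients who cannot be reached stay missing), imputation is not planned for outcomes, and a sandwich estimator cannot bring earlier scores into the T2 estimate.

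**Conclusion.** The point holds in a limited form. The survey paragraph leaves open whether visits are modelled separately or jointly, and it names no visit or patient effect. On the natural reading the T2 estimate does not draw on a patient's earlier scores. It therefore falls short of the use of incomplete data described in section 9.4.2 and of the all-available-data intention in section 9.4.3, and it needs more than missing at random.

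The T2 standard error is 8–15% above complete data for 15–25% missing. Bias is about 0.07–0.15 SD under the assumed one-arm dependence and about 0 if drop-out works alike in both arms. These sizes rest on assumed correlations and drop-out strength, and 25% is the highest of the plan's three missingness figures. The pooled reading adds an error of unknown direction. Only secondary endpoints are affected, but a clearly better analysis is available on data already collected, so the change should be made.

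**What to change.** For each survey score, replace the paragraph with one repeated-measures linear mixed model:
- baseline, 3-month and T2 scores as outcomes;
- visit and arm-by-visit terms, with baseline means constrained equal between arms;
- site;
- unstructured within-patient covariance;
- mentor and facility intercepts kept, with the mentor coding of control patients stated.

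Read the 3-month and T2 contrasts from this model.

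The cost is SAP wording and modest programming. The extra random effects may cause convergence problems, so name a fallback covariance structure in advance. The SAP should also state that, for patients who die before T2, the T2 contrast is model-based.

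A side point: section 9.4.2 proposes to examine whether missingness is at random or informative, which observed data cannot settle. A delta-shift sensitivity analysis of the T2 contrast would be a usable, optional substitute.
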